10.4 Analysis of secondary objectives

The assessment of superiority of Edoxaban will be assessed if the primary endpoint analysis shows non-inferiority. In this case, the test will use the same methodology but will test the hypothesis that the difference in bleed rates (Warfarin – Edoxaban) is significantly different from zero rather than significantly greater than -1.5%.

With the exception of continuous change in hemoglobin, all remaining secondary endpoints are binary. They will be summarized with the number and percent in each group, and as rates based on the total patient-years of follow-up. The treatments will be compared as for the primary endpoint. If there are sufficient numbers of events, survival analysis techniques will also be used.

Continuous change in hemoglobin will be compared using ANCOVA, adjusted for baseline and trial stratification factors.

A statistical analysis plan (SAP) containing more information about end of study statistical analyses will be finalized prior to database lock.

10.5 Populations for analysis

The main populations for analysis will be as follows:

- The **intention-to-treat** population will include all randomized subjects, grouped by randomized treatment assignment. Since randomization occurs on the day of the procedure, all randomized subjects are expected to undergo device implant.

The primary and secondary endpoints will be evaluated in the intention-to-treat population. Adverse events and other safety information will be reported for all subjects where the implant procedure was started.

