DURATION OF PATIENT PARTICIPATION AND DURATION OF STUDY	
Screening: 7-26 days
 
Treatment: 5 days of randomized therapy prior to procedure (which is a single day)
 
Follow-up: 180 days

CONCOMITANT MEDICATIONS	Allowed as per approved FDA guidelines
EFFICACY EVALUATIONS	
PRIMARY ENDPOINT	Major local or systemic bleeding as defined in the protocol at 30 days after implant procedure
SECONDARY ENDPOINTS	The secondary objectives are to compare the rates of thrombotic events (embolism or stroke) through 6 months following the procedure in the Edoxaban and Warfarin groups and the rates of MACE events through 6 months following the procedure in the Edoxaban and Warfarin groups
OTHER EVALUATIONS	The exploratory objectives are to compare rates of hemoglobin reductions from pre-procedure to 24-48 hours post procedure in the Edoxaban and Warfarin groups
SAFETY EVALUATIONS	Safety monitoring during the study will be performed by an independent data monitoring committee (DMC), as well as medical and clinical monitors

	and the coordinating center. Sites will be monitored by a clinical monitor at least once during this short trial. Clinical sites will be required to report all procedure related complications, deaths and major adverse events to the medical monitor within 24 hours of learning of the event. All events will be adjudicated by an independent events committee.
PLANNED INTERIM ANALYSES	When approximately 200 subjects have completed the study through the 30-day visit, an interim analysis for safety will be conducted by an independent data monitoring committee. Serious adverse events will be monitored by the committee on an ongoing basis throughout the study. Based on the primary outcome in these 200 subjects, the study may continue to enroll up to 200 additional subjects, or be terminated.
STATISTICS Primary Analysis Plan	This study contains an internal pilot, and the primary endpoint will be evaluated when 200 patients have reached 30-days post procedure or withdrawn. Based on the primary outcome in these 200 patients, the study may enroll up to 200 additional subjects, or be terminated. Bleeding rates will be compared for non-inferiority using a 1-sided exact test (Primary Endpoint). If non-inferiority of Edoxaban is demonstrated, superiority will be assessed using a 2-sided exact test (Secondary Endpoint).

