3.2 Secondary Objective

The secondary objectives are:

1. To compare the rates of thrombotic events (embolism or stroke) through 6 months following the procedure in the Edoxaban and Warfarin groups
2. To compare the rates of MACE events through 6 months following the procedure in the Edoxaban and Warfarin groups

MACE components include:

- Cardiovascular hospitalization
- Stroke

- Myocardial infarction
- Heart failure
- Vascular events
- Death

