4.1 Overview

This study is a randomized, open label, active-controlled trial with a safety extension (follow-up phase). It is designed to compare bleeding, local or systemic, within 30 days of cardiac rhythm device implant (acute phase) for non-valvular AF among patients randomized to continuous Warfarin or interrupted

Edoxaban. Randomization will be stratified by device type and HAS-BLED score (≤ 2 or ≥ 3). Patients will be randomized in a 1:1 ratio to receive interrupted Edoxaban or continuous Warfarin. This study contains an internal pilot opportunity to adjust the sample size or terminate the study, and there will be an interim analysis of the primary endpoint when 200 patients have reached 30-days post procedure or withdrawn. Based on the primary outcome in these 200 patients, the study may:

[figure not shown]
- Enroll 200 additional patients (pacemaker capped at 100 patients, ICD capped at 150 patients)
- Enroll 100 additional patients
- Be terminated

The study design is outlined in Figure 1.

Figure 1:

Study Design Flow Chart

Study Timeline

- Seamless design, enrollment does not stop between phases
-  Opportunity to stop if Part I objectives are not met
- Minimal resource commitment to Part II if Part I objectives not met
- For Part II, all sites enrolling, experience should lead to improved data quality compared to Part I
- Phases analyzed separately (primary) and combined

Eligible subjects must be stable on a therapeutic dose of Warfarin (INR 2-3) for three weeks prior to randomization. If potential patients are taking an anticoagulant besides Warfarin, or otherwise not meeting this criteria, must be switched to Warfarin and complete 3 weeks of dosing with INRs in the therapeutic range (run-in period) at randomization.

Comment [s1]: Segment into two sentences.
Insert period

Comment [s2]: delete

Comment [s3]: delete

Comment [s4]: Insert

The final INR should be performed on the day of randomization, and the procedure should be scheduled a minimum of 5 days and at most 15 days after randomization. Once eligibility has been confirmed and informed consent has been obtained, patients will be randomized via an interactive secure web randomization system. Patients will be randomized in a 1:1 ratio to Edoxaban or Warfarin. Randomization will be blocked by HAS-BLED score, and based on a randomization list, which will be created prior to commencement of the study.

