6.1.2 Acute Open Label Phase

Subjects eligible for randomization will have maintained INR values in the therapeutic range based on a patient-specific dose of Warfarin – or baseline Warfarin therapeutic dose. From randomization to assessment of the primary endpoint, the study will be open label in design. In subjects randomized to Edoxaban in accordance with drug labeling, the transition from Warfarin and initiating Edoxaban should be performed when the INR has decreased below 2.5 after the discontinuation of Warfarin.

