6.1.3 Follow-up Open Label Phase

[figure not shown]
Subjects randomized to continuous Warfarin should have an INR in the first month, and continue monthly INRs as per standard practice guideline recommendations. Warfarin dosage should be adjusted according to standard practice to keep patients in the therapeutic range. Subjects randomized to Edoxaban should take it once daily per package dosing instructions (Edoxaban 60 mg daily dose for

creatinine clearance 50 to 95 ml/min and Edoxaban 30 mg for creatinine clearance of 30 to 49 ml/min). Subjects will be followed for an additional five months with a phone follow up at 3 months (± 1 week) and final follow up visit at 6 months (± 1 week). After the final follow up visit or after the subject is terminated from the study, subjects on Edoxaban transitioning to Warfarin should be maintained on Edoxaban until the INR is 2.0 or higher before Edoxaban discontinuation in accordance with drug labeling.

7. Study Visits

This study consists of three parts: a run-in or eligibility phase, an acute phase and a follow-up phase. Figure 2 for shows a diagram of study activities. Table 2 and Appendix A show visits.

Figure 2: Study events

Eligibility will be assessed when subjects have completed 3 weeks of Warfarin dosing. The procedure should be scheduled 5 to 15 days after randomization so that subjects are adequately anticoagulated with Warfarin or Edoxaban. The last dose of Edoxaban will be administered less than 24 hours prior to the procedure. Randomization will be obtained via IVRS once eligibility has been confirmed and the procedure has been scheduled.

On the day of the procedure, Warfarin will be continued and Edoxaban will be interrupted. Edoxaban dosing will resume a minimum of 16 and a maximum of 24 hours following the procedure. During and after the procedure, subjects will be assessed for safety and efficacy endpoints for bleeding and

embolism respectively as well as major adverse cardiovascular events (MACE). Edoxaban subjects will in general be discharged on the same day as the procedure, whereas Warfarin subjects will have their discharge timing determined on an individual basis by the investigator.

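### Section 10.5 wrongly places randomization on the procedure day, so its final safety tables leave out randomized subjects whose procedure never started, and their endpoint status is not stated

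*Combined protocol and SAP*

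**What the plan says.** All references are to the combined protocol and SAP.

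**Timing.** Section 10.5 states: "Since randomization occurs on the day of the procedure, all randomized subjects are expected to undergo device implant". Section 4.1 instead says that "the procedure should be scheduled a minimum of 5 days and at most 15 days after randomization". Section 7 agrees: "The procedure should be scheduled 5 to 15 days after randomization so that subjects are adequately anticoagulated with Warfarin or Edoxaban". The synopsis, under duration of participation, lists "5 days of randomized therapy prior to procedure (which is a single day". Section 4.1 also has the 30-day kit of assigned drug handed over at the randomization visit. For the Edoxaban arm, 6.1.2 says that "initiating Edoxaban should be performed when the INR has decreased below 2.5 after the discontinuation of Warfarin".

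**Analysis sets.** Section 10.5 analyses the primary and secondary endpoints in all randomized subjects by assigned arm. It reports adverse events and other safety data only for subjects whose implant procedure had begun.

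**Collection.** Section 8.1 asks for every adverse event after randomization to be entered on the CRF. Section 8 sends adverse events to the DSMB in tables, without limiting them to subjects who reached the procedure.

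**Endpoints.** The synopsis gives the primary endpoint as "Major local or systemic bleeding as defined in the protocol at 30 days after implant procedure". The first secondary objective in 3.2 is "To compare the rates of thrombotic events (embolism or stroke) through 6 months following the procedure"; MACE runs over the same period. Section 10.6 promises sensitivity analyses for missing data and leaves the imputation algorithms to the SAP.

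**The concern.** The sentence in 10.5 is more than a slip of wording, because the analysis sets depend on it. If randomization and procedure fell on the same day, randomized subjects and subjects with a started procedure would be nearly the same people, and the choice between the two sets would hardly matter. With 5 to 15 days between them, and assigned drug taken in that time, the sets differ.

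The subjects who fall between the sets are not necessarily a random few. All subjects are on Warfarin at randomization, and only the Edoxaban arm changes anticoagulant before the procedure. A bleed or stroke in that window could cancel the procedure. That subject's event would then be on the CRF but outside the final safety tables, and the omission could differ by arm. At stake is a complete safety comparison of the two assigned strategies.

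The second gap is the endpoint. A subject with no procedure has no 30th day after it, yet stays in the denominator. The plan does not say whether such a subject counts as event-free or missing, or whether a bleed on assigned drug before the planned procedure counts. Few Edoxaban events are expected and the trial is open label, so the rule should be fixed in advance.

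**Working it through.** **1. Timing, side by side.**

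| Place | Randomization relative to procedure |
|---|---|
| 10.5 | same day |
| 4.1 | 5 to 15 days before |
| 7 | 5 to 15 days before |
| Synopsis, duration | 5 days of assigned therapy first |
| 4.1, drug supply | kit given at the randomization visit |

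Only 10.5 differs. The other entries describe how the trial is to be run.

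**2. What the 10.5 safety rule keeps and drops.**

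| Subject | Final safety tables | DSMB tables |
|---|---|---|
| Procedure started, including failed implants | in, with adverse events from before the procedure | in |
| Randomized, procedure never started | out | in |

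**3. How many subjects.** Appendix B shows 343 randomized to continuous Warfarin in the source trial, of whom 8 had no procedure.

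- Share: 8/343 = 2.33%; Clopper-Pearson 95% interval 1.01% to 4.54%.
- Of 300: 300 × 0.0233 = 7.0 (3.0 to 13.6).
- Of 400: 400 × 0.0233 = 9.3 (4.0 to 18.2).

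Applying this share here is an assumption. The interval reflects sampling error only.

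**4. Effect on power.** Inputs from sections 10 and 10.2: rates 3.51% and 0.5%, margin 1.5%, one-sided 0.025, 150 per arm.

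Reproducing the plan's figure with unpooled variance:
- Distance: 1.5% + 3.51% − 0.5% = 4.51%.
- Standard error: √[(0.0351 × 0.9649 + 0.005 × 0.995)/150] = 1.609%.
- Power: Φ(4.51/1.609 − 1.96) = Φ(0.84) = 80.0%, against the approximately 80% stated.

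An exact unconditional test ordered by the Farrington-Manning score gives 79.6%. This form is assumed, because 10.3 says only that the test is exact.

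| No-procedure subjects, 150 per arm | Unpooled | Exact |
|---|---|---|
| None | 80.0% | 79.6% |
| 2.33%, scored event-free | 79.7% | 79.0% |
| 2.33%, excluded | 79.1% | 79.1% |
| 4.54%, scored event-free | 79.4% | 78.4% |

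For the event-free rows both rates are multiplied by (1 − share). For the excluded row the arm size is 150 × 0.9767 = 146.5 (147 in the exact test). At the observed share the loss is under one point on either scoring. At the upper confidence limit it is 79.6 − 78.4 = 1.2 points.

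**5. Why the endpoint rule can still matter.** Expected Edoxaban events at 150 per arm are 0.005 × 150 = 0.75. With the same assumed exact test, 0, 1, 2 or 3 Edoxaban events need at least 2, 4, 6 or 8 Warfarin events for non-inferiority. Each Edoxaban event counted or not counted moves the requirement by two Warfarin events.

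**The case against.** The strongest reply is that this is a small matter the SAP can settle. A procedure-started safety set is a recognisable choice in a peri-procedural trial. The omitted events are still collected and go to the DSMB. The SAP must be final before database lock, and 4.2.3 provides blinded adjudication of potential primary events. The source trial's ITT row in Appendix B also carries its 8 no-procedure patients with 0 bleeds, which hints at a scoring rule. Randomization here happens only once the procedure has been scheduled (section 7), so the 2.3% share may not carry over.

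Much of this stands. The endpoint gap is secondary, since one SAP sentence could close it, and the counts are not a forecast. But the safety set is a stated rule that rests on a wrong premise, so leaving detail to the SAP does not correct it. Nor does the plan adopt the Appendix B scoring for this trial.

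Some stronger readings are tempting but not supported:

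- **That all events before the procedure are lost.** Subjects who reach the procedure keep theirs in the tables.
- **That safety oversight is blind to these events.** Section 8 sends them to the DSMB.
- **That the 3.51% planning rate is unsound because its case-mix rows total 335 (98 + 58 + 106 + 73), the patients who had the procedure.** Appendix B prints the ITT rate beside it, 12/343 = 3.50%, and nothing links the weighting to the sentence in 10.5.
- **That 10.5 guarantees every subject an implant.** It states an expectation, so calculating the chance that all 300 are implanted would test a claim the plan does not make.
- **That the trial is underpowered as a result.** The shift is too small.

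**Conclusion.** The point holds and should be fixed. Section 10.5 contradicts 4.1, 7 and the synopsis on when randomization occurs. As written, its safety rule removes from the final comparison adverse events that the trial has already collected in randomized subjects whose procedure never started. The endpoint status of those subjects is also unstated.

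About 7 of 300 or 9 of 400 subjects would be affected if the source trial's 2.3% applies here. The documents give no probability for an event that cancels the procedure, so its effect on the safety comparison, and any difference between arms, cannot be quantified. Sample size needs no change on this account.

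**What to change.** 1. Correct the sentence in 10.5 so that it agrees with 4.1, 7 and the synopsis.
2. Report adverse events and other safety data from randomization for all randomized subjects by assigned arm. Keep the procedure-started set as supplementary.
3. State the primary and secondary endpoint status of randomized subjects with no procedure.
4. Add a sensitivity analysis counting adjudicated major bleeds from randomization in all randomized subjects. Leave the procedure-timed primary endpoint as it is.

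**Cost.** Wording, a few more tables, and safety results that may look slightly less favourable. Items 2 and 4 use data already collected under 8.1. On adjudication, the synopsis says "All events will be adjudicated by an independent events committee"; 4.2.3 names only potential primary endpoint events, so the text should make clear that bleeds before the procedure go to the committee.

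**Limit.** The same cannot be promised for thrombotic events and MACE. The 30-day, 3-month and 6-month contacts are timed from the procedure (4.1 and 7). A subject without one has no scheduled contact beyond a final visit at discontinuation, where feasible. These outcomes can be counted only as far as they are captured, and the report should say so.

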9.2 Site training and monitoring

Prior to study initiation, all investigators and research coordinators will be trained in the study protocol at a central investigators meeting. Each clinical site will be visited by trained clinical monitors at least once during the study to make sure that study protocol procedures are being followed, consent is being

obtained per regulation and data are being collected contemporaneously and accurately. Clinical monitoring visits will be scheduled as needed thereafter. Any serious complications of the implant procedure will be reviewed by the DMC and a summary of the failures and complications will be presented to the DMC at each meeting.

10. Assessment of Non-Inferiority Hypothesis and Data Analysis

This study was designed based on a non-inferiority hypothesis, with an overall type I error rate of 0.025 (1-sided). The non-inferiority margin is 1.5%.

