10.1 Expected event rates

See section 5.1 for case mix assumptions. For Warfarin, the 30-day primary event rate is estimated to be 3.51 % based on the continuous Warfarin arm of the BRUISE control study⁽³⁾. For Edoxaban, we estimate the primary endpoint rate to be 0.5%. In the Danish study by Kirkfeldt⁽⁴⁾, major perioperative hematomas requiring re-intervention was 0.2% for new implants and 0.1% for generator changes. In this study, 26.6% of implants were ICDs and 73.4% were pacemakers. In the report by Dewland from the NCDR registry, ICD hematoma rates were estimated at 0.8% for new implants. Using the case mix assumptions in section 5.1, 30% new ICDs, 20% new pacemaker implants, 30% generator changes only, and 20% pulse generator changes and lead revisions, the estimate is more conservative (lower).

Details of this calculation and comparison to other studies can be found in Appendix A

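### Non-inferiority is tested in the intention-to-treat set alone, on a same-day randomization premise that the schedule contradicts; add a supportive per-protocol analysis

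*Combined protocol and SAP*

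**What the plan says.** Section 10.5 lists one main population, all randomized subjects grouped as assigned, and says: "The primary and secondary endpoints will be evaluated in the intention-to-treat population". A set of patients whose procedure was started is mentioned, but only for adverse events and other safety reporting. The supporting analyses are a stratified Cochran–Mantel–Haenszel test (10.3) and sensitivity analyses for missing data (10.6). Neither concerns the drug actually received. Section 10.4 defers further detail to a SAP to be finalized before database lock.

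Section 10.5 supports its choice by placing randomization on the day of the procedure and expecting all randomized subjects to be implanted. Section 4.1 says "the procedure should be scheduled a minimum of 5 days and at most 15 days after randomization", and Section 7 repeats the 5 to 15 day interval. The synopsis gives 5 days of randomized therapy before the procedure.

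All patients come to randomization on therapeutic Warfarin (4.1). Only the Edoxaban arm changes drug before surgery: "the transition from Warfarin and initiating Edoxaban should be performed when the INR has decreased below 2.5" (6.1.2).

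**The concern.** Intention-to-treat keeps the comparison randomized, but in a non-inferiority trial it is not conservative in every situation. Patients who have no procedure, or who are operated on under the other arm's drug, pull the two bleeding rates together. If Edoxaban truly causes more bleeding, the observed excess shrinks and a false claim becomes more likely.

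The plan leaves room for this. There are up to 15 days between randomization and surgery, treatment is open label, and one arm must complete a drug switch that the other does not. The reason given in 10.5 for expecting full treatment fails on the protocol's own schedule. At stake is whether a non-inferiority finding can be read as a statement about interrupted Edoxaban at surgery, or only about assignment to it.

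**Working it through.** **Inputs from the documents**
- Margin 1.5 percentage points, one-sided error 0.025 (Section 10, opening). The hypothesis is that Warfarin minus Edoxaban exceeds −1.5% (10.4).
- Warfarin rate 3.51%, Edoxaban rate 0.5% (10.1).
- 300 patients for about 80% power (10.2), 1:1, so 150 per arm. The maximum of 400 gives 200 per arm.
- No procedure after randomization: 8 of 343 = 2.3%, with no bleeds, in the source arm of Appendix B.

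**Assumptions**
- The documents give no crossover rate. I use f = 10%, 20% and 30% of the Edoxaban arm operated on under Warfarin, at Warfarin risk.
- Patients without a procedure count as event-free, as in Appendix B's source.
- The documents say only that the test is exact. I use the unconditional exact test ordered by the Farrington–Manning score.

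**1. The plan's own figure.** Normal approximation, 150 per arm:
- SE = √[(0.0351 × 0.9649 + 0.005 × 0.995)/150] = 0.0161
- z = (0.0351 − 0.005 + 0.015)/0.0161 − 1.960 = 0.843
- Power = 80.0%. The stated size reproduces.

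The exact test gives 79.6% at 150 per arm and 91.8% at 200.

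**2. Edoxaban truly at the margin (5.01% v 3.51%).** With dilution:
- Warfarin arm: pW = 0.0351 × 0.9767 = 3.43%
- Edoxaban arm: pE = pW + 0.015 × (1 − f) × 0.9767

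Chance of wrongly declaring non-inferiority, exact test:

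| Scenario | Apparent excess, points | 150 per arm | 200 per arm |
|---|---|---|---|
| No dilution | 1.50 | 2.0% | 2.2% |
| 2.3% no procedure, f = 10% | 1.32 | 2.4% | 2.8% |
| 2.3% no procedure, f = 20% | 1.17 | 2.8% | 3.2% |
| 2.3% no procedure, f = 30% | 1.03 | 3.2% | 3.8% |

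The 2.3% without a procedure, on its own, moves the level at 150 per arm only from 2.0% to 2.1%. If 20% of both arms crossed over, with no missed procedures, it would be 3.6% at 150 per arm.

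**3. Edoxaban better, as planned (0.5% v 3.51%).** With crossover alone, pE = (1 − f) × 0.5% + f × 3.51%. At f = 10%, pE = 0.80%, and exact power at 150 per arm falls from 79.6% to 68.0%. At f = 20%, pE = 1.10% and power is 56.9%.

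**4. A per-protocol test.** If 10% are excluded, 135 per arm remain, and exact power in that set alone is 76.8%. Requiring success in both sets would give joint power of 75.2% if the excluded patients carry their own arm's risk. It would give 65.2% if the excluded Edoxaban patients carry Warfarin risk.

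**The case against.** A reader might infer that testing in intention-to-treat alone pushes this trial towards non-inferiority whatever the truth. The documents do not support that. The direction depends on the true effect: 10.1 expects Edoxaban to be 3.01 points better (3.51 − 0.5), and there dilution works against the claim.

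Other points on that side:

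- **The objective is framed by assignment.** Sections 3.1 and 4.1 compare patients as randomized, and intention-to-treat answers that question with its error rate intact. This stands, and is why intention-to-treat should remain primary.
- **The inflation is small and rests on assumed crossover.** This stands. At 150 per arm and 10% crossover the level, 2.4%, is still under the nominal 2.5%.
- **The later SAP could add the analysis.** Section 10.5 speaks of main populations, which does not exclude a supportive set. But a late SAP cannot recover treatment data that were not collected, nor does it repair the premise in 10.5. It is tempting to add that dosing data will not be collected, since Table 2 has no study-drug row. Table 2 is a visit schedule, with rows for concomitant medication and procedure details, and the CRF is not provided, so that is unproven.
- **Per-protocol sets carry their own bias.** This stands. A bleed can delay the restart of Edoxaban, and haematoma requiring interruption of anticoagulation is itself an endpoint component (4.2.1). A set defined by restart time could selectively drop Edoxaban patients who bled, which would favour non-inferiority.
- **Both sets need not be required to meet the margin.** Nothing in the documents calls for it, and the joint power above shows that the cost could be considerable.

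**Conclusion.** The point holds in a limited form. The firm documentary fault is that 10.5 rests its expectation of full implantation on same-day randomization, while 4.1 and 7 put 5 to 15 days between the two. The analysis gap follows: no pre-specified analysis shows whether the non-inferiority result survives among patients operated on under their assigned drug.

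The size is modest. With Edoxaban at the margin, the false-claim rate rises by 0.4 to 1.2 points at 150 per arm (from 2.0% to between 2.4% and 3.2%) and by 0.6 to 1.6 points at 200 per arm (from 2.2% to between 2.8% and 3.8%). These figures depend on the assumed 10–30% one-way crossover; only the 2.3% without a procedure has a source in the documents. Under the planned rates the consequence is lost power. The change is worth making because it is cheap and bears on how the trial's main claim can be read. The choice of intention-to-treat as the primary set is not itself an error.

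**What to change.** 1. Keep intention-to-treat as the primary set. Correct the randomization-day sentence in 10.5 so that it agrees with 4.1 and 7.
2. Add a supportive per-protocol set to 10.5, defined only by facts fixed before or at the procedure: procedure started, and assigned anticoagulant the one in use at the procedure. Do not use post-procedure restart timing to define it.
3. In 10.3, run the same exact test at the 1.5% margin, with its confidence interval, in that set. Report both results and qualify the non-inferiority conclusion if they disagree, without a formal rule that both must succeed.
4. Record the drug and time of the last pre-procedure dose on the CRF, if it is not already captured.
5. Separately, reconcile the two Edoxaban resumption windows: 12 to 24 hours after the procedure in Section 2, and 16 to 24 hours in Section 7.

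The cost is protocol and SAP wording, one more analysis and a small amount of data entry. The intention-to-treat sample size of 300 does not change. The per-protocol set is smaller (76.8% power alone at 135 per arm) and open to selection bias, so it supports intention-to-treat and does not replace it.
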